13.5 STUDY RECORD RETENTION

All study documentation will be kept for a minimum of 5 years from the protocol-defined end of study point. Patient identifiable information will be kept beyond 5 years to facilitate longer term follow up if necessary (this will be made explicit on

consent forms and patient information sheets). When the minimum retention period has elapsed, study documentation will not be destroyed without permission from the sponsor.

13.6 END OF STUDY

It is anticipated that the study will last 4-5 years: three years for recruitment and 15 months of follow-up. The end of study is defined as 15 months after the last participant's last visit. However, longer term follow-up using record linkage may be performed at 5 and 10 years. The Investigators, trial management group and/or the co-sponsor(s) have the right at any time to terminate the study for clinical or administrative reasons. The end of the study will be reported to the REC, Regulatory Authority, R&D offices and co-sponsors within 90 days, or 15 days if the study is terminated prematurely. The Investigators will inform participants of the premature study closure and ensure that the appropriate follow up is arranged for all participants involved. End of study notification will be reported to the co-sponsors via email to [contact]. In accordance with ACCORD SOP CR011, a Clinical Study Report (CSR) will be provided to the Sponsor ([contact]) and REC within 1 year of the end of the study. Upon completion of the study, the Chief Investigator will upload clinical trial results onto the EudraCT database on behalf of the Sponsor.

13.7 INSURANCE AND INDEMNITY

The co-sponsors are responsible for ensuring proper provision has been made for insurance or indemnity to cover their liability and the liability of the Chief Investigator and staff.

The following arrangements are in place to fulfil the co-sponsors' responsibilities:

The Protocol has been designed by the Chief Investigator and researchers employed by the University and their collaborators. The University has insurance in place (which includes no-fault compensation) for negligent harm caused by poor protocol design by the Chief Investigator and researchers employed by the University.

Sites participating in the study will be liable for clinical negligence and other negligent harm to individuals taking part in the study and covered by the duty of care owed to them by the sites concerned. The co-sponsors require individual sites participating in the study to arrange for their own insurance or indemnity in respect of these liabilities. Sites will have the benefit of NHS Indemnity.

The manufacturer of the IMP has accepted limited liability related to the manufacturing and original packaging of the study drug and to the losses, damages, claims or liabilities incurred by study participants based on known or unknown Adverse Events which arise out of the manufacturing and original packaging of the study drug.

14. REPORTING, PUBLICATIONS AND NOTIFICATION OF RESULTS

14.1 AUTHORSHIP POLICY

Ownership of the data arising from this study resides with the study team. On completion of the study, the study data will be analysed and tabulated, and a clinical study report will be prepared in accordance with ICH guidelines.

14.2 PUBLICATION

The Clinical Study Report (CSR) will be submitted to the Sponsor and REC within 1 year of the end of the study. Where acceptable, a published journal article may be submitted as the CSR. The Chief Investigator will provide the CSR to ACCORD, for review, prior to finalization. The clinical study report may be used for publication and presentation at scientific meetings. Investigators have the right to publish orally or in writing the results of the study. The results of the study, together with other mandated information, will be uploaded to the European clinical trials database within 1 year of the end of the study.

14.3 DATA SHARING

Following publication of the primary paper, a de-identified individual participant data set will be submitted to a data archive for sharing purposes. Access to the de-identified dataset will be under a controlled access model in line with ECTU policies at that time.

14.4 PEER REVIEW

The study protocol has undergone independent review by an Edinburgh Clinical Trials Unit statistician and by the British Heart Foundation. The protocol has been amended in accordance with their recommendations.

SD	Standard deviation
SOP	Standard operating procedure
TCL	Total cholesterol
TRE	Trusted research environment
TRI	Triglycerides
UK	United Kingdom

1. Introduction

This document details the criteria to be used for the definitions of the analysis populations and the statistical methodology for analysis of the Dual-ACS trial, a prospective multicentre national open-label randomised controlled trial comparing the duration of dual antiplatelet therapy. The aim is to randomise 18,318 patients with type I myocardial infarction (MI) to 12 or 3 months of dual antiplatelet therapy in a 1:1 ratio. Randomisation is by permuted-blocks with a level of stratification for each of the following groups of patients:

- (i) conservative non-invasive strategy (invasive coronary angiography is not planned),
- (ii) invasive coronary angiography is planned but has not yet occurred,
- (iii) an invasive coronary angiogram has been performed and the patient has been referred or undergone coronary artery bypass grafting (CABG) surgery,
- (iv) an invasive coronary angiogram has been performed and the patient has had at least one drug eluting stent implanted,
- (v) an invasive coronary angiogram has been performed and the patient has had only bare metal stents implanted,
- (vi) an invasive coronary angiogram has been performed and the patient is to receive medical management only.

Recruitment in the United Kingdom (UK) was halted after 4,576 patients because the funder felt the trial was no longer deliverable due to the challenging environment of the COVID-19 pandemic. The statistical analysis will include the patients recruited in the UK and as many international patients who have completed 15 months follow-up at the time of analysis.

This document has been compiled according to the Edinburgh Clinical Trials Unit (ECTU) standard operating procedure (SOP) “ECTU_SOP_ST_04 Statistical Analysis Plans v7.0” and has been written based on information contained in the study protocol version 6.0, dated 22nd July 2022.

2. Statistical Methods section from the protocol

“For the primary outcome (all-cause mortality) we will compare time-to-event in a Cox regression model, stratifying by country and centre to account for clustering of participants, and adjusting for cardiac history (stratification factor in randomisation). For secondary outcomes of non-cardiovascular mortality and bleeding death, we will similarly estimate cause-specific hazard ratios, censoring for competing causes of death. All analyses will be by intention-to-treat.

It is highly likely that baseline characteristics will have a major influence on the overall clinical benefits and risks [Steg et al, 2011]. We will explore efficacy and safety outcomes in the 4 pre-specified and stratified cohorts nested within the trial: (i) medically managed, (ii) percutaneous

Statistical Analysis Plan	Dual-ACS
Version No	V2.0
Date Finalised	4 th Jun 2025

coronary intervention with bare metal stent, (iii) percutaneous coronary intervention with drug-eluting stent, and (iv) coronary artery bypass graft surgery.

In a sensitivity analysis, we will consider a two-stage individual participant data (IPD) meta-analysis where the IPD from each country are analysed separately then combined by an appropriate fixed-effect or random effects meta-analysis model [Burke et al, 2017].

The statistical methods will be documented in full in a detailed statistical analysis plan. The methods used will take into account the early stopping of the trial, and the limited numbers of events that will be available for analysis. A composite outcome of non-fatal bleeding and all-cause mortality will be explored.”

3. Overall Statistical Principles

All analyses will be based on the intention to treat (ITT) principle as far as possible. Patients will be analysed according to their allocation intervention, irrespective of whether the patient's actual management complied with the allocated intervention.

In general terms, categorical data will be presented using counts and percentages, whilst continuous variables will be presented using the mean, median, standard deviation (SD), minimum, maximum, inter quartile range (IQR) and number of patients with an observation (n).

All applicable statistical tests will be 2-sided and presented with 95% (2-sided) confidence intervals (CIs) and a 5% significance level.

Where there is missing data for an outcome variable, in the first instance, those records will be removed from any formal statistical analysis relating to that outcome variable, unless otherwise specified. A sensitivity analysis using imputation of missing values will be considered only if the proportion of cases with missing values is sufficiently large. In tabulations, numbers of missing observations will be provided, but percentages will not include them.

Distributional assumptions underlying the statistical analyses will be assessed by visual inspection of residual plots. Normality will be examined by normal probability plots. If the distributional assumptions for the parametric approach are not satisfied, further data transformation (to alleviate substantial skewness (i.e. log-transformation) or to stabilise the variance), or other suitable methods will be considered. This will be documented in the statistical results report together with the reasoning supporting the action taken, if applicable.

All analyses and data manipulations will be performed using the latest available version of SAS software within the Trusted Research Environment (TRE).

4. List of Analyses

4.1 ITT analysis population

The ITT analysis population will include patients who have been randomised into the Dual ACS trial in the UK and New Zealand (NZ) and for whom outcome data are available. Those who subsequently became ineligible after a diagnosis other than Type 1 myocardial infarction (MI) and withdrawn from the trial will be excluded¹.

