5.5 RANDOMISATION

5.5.1 Randomisation Procedures

A web-based computer-generated randomisation process will be used to ensure allocation concealment and reduce bias. The randomisation system will be provided by ECTU and patients will be randomised using their unique health identifier to prevent inadvertent duplicate randomisation. International sites will use their own randomisation system which will be described in their country specific protocol. Randomisation will be by permuted-block with a level of stratification for

each of the following groups of patients: (i) conservative non-invasive strategy (invasive coronary angiography is not planned), (ii) invasive coronary angiography is planned but has not yet occurred, (iii) an invasive coronary angiogram has been performed and the patient has been referred or undergone CABG surgery, (iv) an invasive coronary angiogram has been performed and the patient has had at least one drug eluting stent implanted, (v) an invasive coronary angiogram has been performed and the patient has had only bare metal stents implanted (this group will also include patients who have had balloon angioplasty only performed without stent implantation), (vi) an invasive coronary angiogram has been performed and the patient is to receive medical management only.

Block size will be randomly determined, and each block will contain both treatments in a 1:1 ratio.

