5.5.3 Methods to Ensure Blinding

This is an open-label trial and there will be no masking of treatment allocation or need for unblinding.

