5.6 WITHDRAWAL OF STUDY PARTICIPANTS

Participants are free to withdraw from the study at any point or a participant may be withdrawn by the attending clinician. If a participant wishes to withdraw they will need to contact their local research team who will document the nature and primary reason for withdrawal, if possible. The contact details for the local site will be provided on a study card. Unless the participant specifically withdraws consent any data collected up to the point of withdrawal will be retained and analysed and data will continue to be collected remotely from the participant's medical notes and via data linkage.

Participants who withdraw or are withdrawn from the study will not be replaced.

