9.3 PROPOSED ANALYSES

For the primary outcome (all-cause mortality) we will compare time-to-event in a Cox regression model, stratifying by country and centre to account for clustering of

participants, and adjusting for cardiac history (stratification factor in randomisation). For secondary outcomes of non-cardiovascular mortality and bleeding death, we will similarly estimate cause-specific hazard ratios, censoring for competing causes of death. All analyses will be by intention-to-treat.

It is highly likely that baseline characteristics will have a major influence on the overall clinical benefits and risks [Steg et al, 2011]. We will explore efficacy and safety outcomes in the 4 pre-specified and stratified cohorts nested within the trial: (i) medically managed, (ii) percutaneous coronary intervention with bare metal stent, (iii) percutaneous coronary intervention with drug-eluting stent, and (iv) coronary artery bypass graft surgery.

In a sensitivity analysis, we will consider a two-stage individual participant data (IPD) meta-analysis where the IPD from each country are analysed separately then combined by an appropriate fixed-effect or random effects meta-analysis model [Burke et al, 2017].

The statistical methods will be documented in full in a detailed statistical analysis plan. The methods used will take into account the early stopping of the trial, and the limited numbers of events that will be available for analysis. A composite outcome of non-fatal bleeding and all-cause mortality will be explored.

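### The SAP's ITT population drops randomised patients who are re-diagnosed and withdrawn, which can bias the mortality comparison and contradicts the protocol

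*SAP*

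**What the plan says.** SAP 4.1 defines the ITT analysis population as patients randomised in the UK and New Zealand "for whom outcome data are available". It then adds: "Those who subsequently became ineligible after a diagnosis other than Type 1 myocardial infarction (MI) and withdrawn from the trial will be excluded". Both conditions must hold: a changed diagnosis and withdrawal.

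Footnote 2, attached to SAP 4.5, says that outcome data up to the point of withdrawal will not be held, and that withdrawn participants are therefore left out of the analysis. As worded, it covers every withdrawal, whatever the reason.

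The protocol says otherwise. Section 9.3 states "All analyses will be by intention-to-treat", with no exception. Sections 4.1 and 9.1 say that the analysis will include the 4,576 UK patients. Section 5.6 provides that, unless consent is specifically withdrawn, "data will continue to be collected remotely from the participant's medical notes and via data linkage". SAP section 3 is softer: "All analyses will be based on the intention to treat (ITT) principle as far as possible".

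Two further provisions bear on how the exclusion would work. Protocol 5.5.3: "This is an open-label trial and there will be no masking of treatment allocation or need for unblinding". Protocol 5.6: "Participants are free to withdraw from the study at any point or a participant may be withdrawn by the attending clinician".

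**The concern.** The rule selects on something that happens after randomisation, when the allocation is known to the clinician who may withdraw the patient. The discretionary part is the withdrawal. Of two patients with the same revised diagnosis, the one who is withdrawn leaves the primary analysis and the other stays.

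Pressure to withdraw might differ by arm, for example if a longer remaining course prompts more action once the diagnosis has changed. If the patients removed also have a different mortality, the retained arms are no longer comparable. The effect would fall on all-cause mortality, the one outcome the trial is designed around.

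Excluding patients found to be ineligible can be defended when the decision is made blind to allocation and uses only information from before randomisation. The SAP requires neither and sets no time limit. It also does not flag the rule as a departure from the protocol, although it does so for dropping centre (footnote 3) and haemoglobin (footnote 4).

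**Working it through.** **1. Which patients leave, and by which rule**

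| Patient | SAP 4.1 sentence | SAP footnote 2 | Protocol 5.6 and 9.3 |
|---|---|---|---|
| Re-diagnosed, not withdrawn | stays | stays | stays |
| Re-diagnosed and withdrawn, consent to data kept | out | out | stays, followed by linkage |
| Withdrawn for another reason, consent to data kept | not addressed | out | stays, followed by linkage |

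Everyone caught by the 4.1 sentence is also caught by footnote 2. Deleting that sentence alone would restore nobody.

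**2. Whether another provision repairs it.** Footnote 1 is attached to the exclusion sentence and speaks of including all participants. In context it concerns the bypass-surgery and bare-metal-stent groups from protocol 9.1, so it does not cancel the exclusion. The sensitivity analyses in SAP 4.5.2 (two-stage meta-analysis, 3-month landmark, centre) do not bring these patients back. SAP 4.2 tabulates withdrawals by reason and arm, but only descriptively.

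**3. The plan's own figure.** Protocol 9.2 uses 16.9% mortality, risk ratio 0.9 (so 15.21%), two-sided 5% and 85% power. The formula is n = [1.960 × √(2p̄(1 − p̄)) + 1.036 × √(p₁(1 − p₁) + p₂(1 − p₂))]² / (p₁ − p₂)². With p̄ = 0.16055 this is (1.0176 + 0.5380)² / 0.0169² = 8,472 per group, as stated. The sample size is not at issue.

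**4. Size of the possible bias.** The documents give no number, timing or arm split of exclusions, so what follows is assumption. Let M be mortality with no true effect, e the fraction excluded from an arm, and k the mortality of those excluded as a multiple of M. Mortality among those retained is M(1 − ek)/(1 − e). M cancels from the ratio of 3-month to 12-month arm:

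RR = [(1 − e₃k)/(1 − e₃)] ÷ [(1 − e₁₂k)/(1 − e₁₂)]

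| e₃ | e₁₂ | k | RR with no true effect |
|---|---|---|---|
| 1% | 1% | any | 1.000 |
| 1% | 3% | 1 | 1.000 |
| 1% | 3% | 0.5 | 0.990 |
| 1% | 3% | 2 | (0.98/0.99) ÷ (0.94/0.97) = 1.021 |
| 1% | 3% | 3 | (0.97/0.99) ÷ (0.91/0.97) = 1.044 |
| 1.5% | 3% | 2 | (0.97/0.985) ÷ (0.94/0.97) = 1.016 |
| 2.5% | 5% | 2.5 | (0.9375/0.975) ÷ (0.875/0.95) = 1.044 |

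Type I error does depend on M. I assume 2,288 per arm (4,576/2, UK only). For 1% v 3% excluded and k = 2 or 3, the nominal 5% becomes 6.2% or 9.8% at M = 16.9%, and 5.3% or 6.2% at M = 5%. At M = 16.9%, k = 3 means 50.7% mortality among those excluded, which is extreme.

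**5. How many could be affected.** Suppose that 5-40% are randomised before angiography and 5-15% of those are re-diagnosed. Then 4,576 × 0.05 × 0.05 = 11 to 4,576 × 0.40 × 0.15 = 275 UK patients have a revised diagnosis. Only those also withdrawn would be excluded.

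**6. Cost of keeping everyone.** If a fraction d has no type 1 MI and no treatment effect, the target becomes 1 − 0.1(1 − d). That is 0.901 at d = 1% and 0.905 at d = 5%. Power at the planned size falls from 85% to 84.4% and 81.3%. At 2,288 per arm it falls from about 34% to about 32% at d = 5%.

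**The case against.** - **It adds nothing to footnote 2.** This stands. A reader might infer that SAP 4.1 is a separate rule removing patients whose outcomes are in hand. The documents do not support that, because footnote 2 already removes every withdrawn participant and says the data will not be held. But footnote 2 conflicts with protocol 5.6 itself, so the overlap widens the repair and does not remove the need for it.
- **The mechanism is speculative.** Partly right. Under protocol 5.5.4 a clinician can change duration without withdrawing anyone, and non-compliance is not logged as a deviation (13.2.3). Both arms are meant to receive the same treatment for the first 3 months, when many diagnoses would be revised. No document says that withdrawal differs by arm. However, allocation is known from the start, and nothing in the plan prevents a difference.
- **Entry already requires a clinical diagnosis of type 1 MI.** True. A reader might infer from the stratum in which "invasive coronary angiography is planned but has not yet occurred" that the trial deliberately randomises before the diagnosis is settled. The documents use that stratum to record angiography status and management group, so linking it to re-diagnosis is inference. What the documents do show is that SAP 4.1 expects some diagnoses to change after randomisation.
- **The bias is small beside the noise.** At 6% mortality and 2,288 per arm, the standard error of the log risk ratio is about 0.12. Ratios of 1.016 and 1.044 are then about 0.13 and 0.35 standard errors, with type I error about 5.2% and 6.4%. That is fair as to size, but the distortion is avoidable at little cost.
- **The SAP claims ITT only as far as possible and reports withdrawals by arm.** An imbalance would be visible, but the primary estimate would not be corrected for it.

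**Conclusion.** The population in SAP 4.1 is wrong as written. It is labelled ITT but lets an unmasked, discretionary decision after randomisation remove patients from the primary analysis, and it contradicts protocol 9.3 and 5.6.

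A reader might infer that the comparison is, or will be, biased. The documents support only that it can be. Bias is nil if exclusion is unrelated to arm, or if those excluded have the same mortality as the rest. With more exclusions in the 12-month arm, it goes against 3 months if those excluded have higher mortality and in favour of 3 months if theirs is lower. The illustrative range of about 1.02-1.04 with no true effect rests on assumed exclusions of 1% v 3%, or 2.5% v 5%, at 2 to 3 times the average mortality. None of these figures comes from the documents. Against a target of 0.90 the shift is modest, but no planned analysis would correct it.

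**What to change.** Make these changes together, before the primary analysis is run:

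1. Delete the diagnosis-and-withdrawal exclusion from SAP 4.1, and amend footnote 2 to match protocol 5.6. The primary analysis then includes every randomised patient as allocated, followed by linkage, and omits only those who withdrew consent to data use. Reword the outcome-availability condition in 4.1 so that it does not bring the exclusion back.
2. Report by arm the numbers re-diagnosed and the numbers excluded, with their deaths where known.
3. Move the type 1 MI restriction to a sensitivity analysis that removes all re-diagnosed patients, withdrawn or not, from a list drawn up blind to allocation.
4. If linkage for some withdrawn patients is truly unobtainable, state the number by arm and bound its effect, for example by assigning their deaths unfavourably to each arm in turn.
5. Move footnote 1 away from the exclusion sentence, where it confuses the meaning.

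The cost is SAP wording, one sensitivity run, and possibly a linkage request if footnote 2 is right that these data are not held. The statistical cost is the slight dilution shown above.

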4.2 Recruitment and retention

Numbers required to complete a CONSORT flow diagram will be provided. The statistical report will tabulate the number of patients consented, randomised, adherent and completed follow-up overall and by treatment group. The number of patients discontinued early from the study will be summarised by reason for withdrawal and treatment.

